7. RATIONALE AND BACKGROUND

Cardiac amyloidosis (CA) is a restrictive cardiomyopathy secondary to amyloid deposits, which are misfolded protein fragments, in cardiac tissue (1, 2).

The most common forms of CA are caused by deposition of monoclonal immunoglobulin light chains (AL) or transthyretin which can be hereditary or acquired (3).

Light chain CA is considered a rare disease with an estimated prevalence between 8-12 cases per million (4). The prevalence of CA in patients with heart failure is estimated at 13.7% (95% CI 7.9 – 19.8) according to a meta-analysis collecting studies worldwide (5). In patients with heart failure preserved ejection fraction, it increases to 15.1% (95% CI 9.6-20.6). Analyzing the subgroup of amyloidosis, the prevalence in patients with wild type transthyretin amyloidosis (wtATTR) was 9.0% (95%CI 5.2 - 12.7) while hereditary transthyretin amyloidosis (ATTRv) was 2.9% (95% CI 0.8-4.9)(5).

The diagnosis of CA is delayed or missed. It has required more than 4 years as is the case of ATTR-CA. Highlighting that 44% of patients with transthyretin amyloidosis (ATTR) and 81% with AL are usually evaluated for more than five physicians before diagnosis (6). The patients with preliminary stages of CA are commonly misdiagnosed with other cardiovascular diseases such as hypertensive cardiac disease, hypertrophy cardiomyopathy, or ischemic heart diseases (7).

The diagnosis of this disease is challenging requiring multidisciplinary management. Additionally, the absence of therapies and late presentation of CA has produced a sub-diagnosis of this condition (4). For that reason, red flags have raised suspicion of AL and allowed a diagnosis to be made. Among them, some red flags are heart failure with preserved ejection fraction, down-titration of anti-hypertensive medication, intracardiac thrombosis, stroke and transient ischemic attack, poor tolerance to heart failure therapy, carpal tunnel syndrome, biceps tendon rupture, lumbar spinal stenosis, trigger finger, polyneuropathy, antihypertensive drugs down-titration, autonomic dysfunction, macroglossia, spontaneous bruising, unexplained left ventricular hypertrophy (>12 mm), right ventricular hypertrophy, increased valve thickness, pericardial effusion, apical sparing, batrial dilation, diastolic dysfunction, elevated B-type natriuretic peptide/N-terminal pro B-type natriuretic peptide (BNP/NT-proBNP) levels, persistently elevated troponin levels, and atrial fibrillation (7).

CA diagnosis is relevant given that it is associated with significant morbidity and mortality. ATTR-CA diagnosis requires several invasive and non-invasive imaging and tests. Electrocardiography, echocardiography, cardiac magnetic resonance imaging for suspicion of CA. Nuclear scintigraphy allows identifying ATTR amyloid deposits and transthyretin (TTR) gene sequence to differentiate between hereditary or acquire ATTR (1). With the availability of scintigraphy, the diagnosis of ATTR-CA has increased exponentially and patients have been diagnosed earlier in the disease course, also by the increased awareness among physicians and specialties (8).

PFIZER CONFIDENTIAL

CT24-WI-GL02-RF01 6.0 Non-Interventional Study Protocol Template For Primary Data Collection Study 01-

Aug-2023

Page 18 of 57

**CLINICAL AND MEDICAL CONTROLLED DOCUMENT (CMCD)
REQUIRED FORM/TEMPLATE**

Identifier	Version	Title	Effective Date
CT24-WI-GL02-RF01	6.0	NON-INTERVENTIONAL STUDY PROTOCOL TEMPLATE FOR PRIMARY DATA COLLECTION STUDY	01-Aug-2023

In terms of healthcare resource, the ATTR-CA has a relevant impact compared to heart failure (HF) patients. One study conducted in four countries using information from databases between 2008 and 2018 found that during the first year after diagnosis, the outpatient visits was higher among transthyretin amyloid cardiomyopathy (ATTR-CM) (10.2 [95%CI 10.1-10.4]) than HF patients 5.7 [95%CI: 5.6 -5.9]) and number of hospitalizations (3.3 [CI: 3.2 - 3.4] vs. 2.5 [CI: 2.5 - 2.6]), hospitalization days (21.7 [CI: 21.5 -22] vs. 15.2 [CI: 15 -15.4]), and surgical procedures (1.7 [CI: 1.6 -1.8] vs. 1.06 [CI: 1.00 -1.12]) (9). Colombia does not have information that evaluates the use of resources in CA.

During the last decade, the treatment option for CA was limited to symptom management. Currently, there other options to manage this disease which can slow disease progression to optimize quality of life and improve survival. There are several types of diseases-modified therapies both researched and approved for use. They depend on the type of CA. For AL-CA, for instances, chemotherapy regimens, immunotherapy, and autologous stem cell transplantation are therapeutic options with several limitations such as toxicity or tolerability by patients. While ATTR-CA, the only therapy approved by the Food Drug Administration (FDA) has been tafamidis, a TTR stabilizer. Other therapies called TTR silencers (inotersen and patisiran) are approved only for polyneuropathy, but in CA are in the clinical phase (10).

Tafamidis was approved by the FDA in May 2019 after positive results of the ATTR-CM study. This study recruited 441 ATTR-CM patients divided into three arms (oral tafamidis 80 mg, tafamidis 20 mg, or placebo). The pooled analysis showed that tafamidis of 80 mg and 20 mg versus placebo were associated with a reduction in all causes of mortality (29.5% vs 42.9%, HR 0.70; CI 0.51-0.96) and cardiovascular hospitalizations (RR 0.68; CI 0.56-0.81) at 30 months. Other endpoints such as functional capacity by six-minute walking test and quality-of-life measured by the Kansas City Cardiomyopathy Questionnaire (KCCQ)–Overall Summary score were notably lower. In terms of tolerability, there were no significant safety problems reported (11). Tafamidis was approved in July of 2022 in Colombia.

Considering that Colombia has already approved tafamidis as an option therapy for ATTR-CM patients, the characteristics of its health care system, the awareness process of the CA in the physicians to diagnostic and treat early, and the limitation of patient compliance to use the therapy, this study intends to measure the impact of tafamidis in quality of life, hospital frequency and mortality during the first two years of follow-up in Colombian patients diagnosed with ATTR-CM.

This non-interventional study is designated as a PASS and is conducted voluntarily by Pfizer.

PFIZER CONFIDENTIAL

CT24-WI-GL02-RF01 6.0 Non-Interventional Study Protocol Template For Primary Data Collection Study 01-

Aug-2023

Page 19 of 57

**CLINICAL AND MEDICAL CONTROLLED DOCUMENT (CMCD)
REQUIRED FORM/TEMPLATE**

Identifier	Version	Title	Effective Date
CT24-WI-GL02-RF01	6.0	NON-INTERVENTIONAL STUDY PROTOCOL TEMPLATE FOR PRIMARY DATA COLLECTION STUDY	01-Aug-2023

8. RESEARCH QUESTION AND OBJECTIVES

Hypothesis

There are not hypotheses to evaluate.

Research Question

What is the impact of tafamidis use in Colombian patients diagnosed with ATTR-CM on quality of life during two years of follow-up?

Primary objective

To describe the impact of tafamidis use in Colombian patients diagnosed with ATTR-CM on quality of life during two years of follow-up

Secondary objectives

- To describe the clinical and demographic characteristics of the patients at the moment of prescription of tafamidis
- To determine the treatment patterns to manage ATTR-CM before tafamidis prescription
- To evaluate the frequency of hospitalization and its causes during the follow-up period
- To describe the use of cardiovascular devices during follow-up of patients recruited in the study
- To outline the change in baseline for patients in cardiovascular functionality in patients prescribed tafamidis
- To measure the adherence of the patients to the therapy
- To describe the access barriers during the use of tafamidis

Exploratory objectives

- To analyze the relationship between baseline variables and patient and changes of quality of life and cardiovascular functionality

PFIZER CONFIDENTIAL

CT24-WI-GL02-RF01 6.0 Non-Interventional Study Protocol Template For Primary Data Collection Study 01-Aug-2023
Page 20 of 57

CLINICAL AND MEDICAL CONTROLLED DOCUMENT (CMCD) REQUIRED FORM/TEMPLATE

Identifier	Version	Title	Effective Date
CT24-WI-GL02-RF01	6.0	NON-INTERVENTIONAL STUDY PROTOCOL TEMPLATE FOR PRIMARY DATA COLLECTION STUDY	01-Aug-2023

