**CLINICAL AND MEDICAL CONTROLLED DOCUMENT (CMCD)
REQUIRED FORM/TEMPLATE**

Identifier	Version	Title	Effective Date
CT24-WI-GL02-RF01	6.0	NON-INTERVENTIONAL STUDY PROTOCOL TEMPLATE FOR PRIMARY DATA COLLECTION STUDY	01-Aug-2023

NON-INTERVENTIONAL (NI) STUDY PROTOCOL

PASS information

Title	Impact of tafamidis use in Colombian patients diagnosed with ATTR-CM on quality of life during two years of follow-up
Protocol number	B3461112
Protocol version identifier	1.0
Date	27 July 2023
EU Post Authorization Study (PAS) register number	EUPAS105913
Active substance	N07XX08
Medicinal product	Tafamidis
Product reference	INVIMA 2022M-0020673
Marketing Authorization Holder(s) (MAH)	Pfizer SAS [name]
Joint PASS	No.
Research question and objectives	
Research Question What is the impact of tafamidis use in Colombian patients diagnosed with ATTR-CM on quality of life during two years of follow-up?
 
Primary Objective To describe the impact of tafamidis use in Colombian patients diagnosed with ATTR-CM on quality of life during two years of follow-up
 
Secondary Objectives
 
• To describe the clinical and demographic characteristics of the patients at the moment of prescription of tafamidis• To determine the treatment patterns to manage ATTR-CM previous to Tafamidis prescription• To evaluate the frequency of hospitalization and its causes during the follow-up period

PFIZER CONFIDENTIAL

CT24-WI-GL02-RF01 6.0 Non-Interventional Study Protocol Template For Primary Data Collection Study 01-Aug-2023
Page 1 of 57

**CLINICAL AND MEDICAL CONTROLLED DOCUMENT (CMCD)
REQUIRED FORM/TEMPLATE**

Identifier	Version	Title	Effective Date
CT24-WI-GL02-RF01	6.0	NON-INTERVENTIONAL STUDY PROTOCOL TEMPLATE FOR PRIMARY DATA COLLECTION STUDY	01-Aug-2023

	
• To describe the use of cardiovascular devices during the follow-up of patients recruited in the study• To outline the change in baseline for patients in cardiovascular functionality in patients prescribed tafamidis.• To measure the adherence of the patients to the therapy.• To describe the access barriers during the use of tafamidis 
Exploratory objectives
 
• To analyze the relationship between baseline variables and changes on quality of life and cardiovascular functionality
Country of study	Colombia
Author	[name] PFIZER S.A.S [contact] [name]

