9.7. Data analysis

9.7.1. Statistical Hypotheses

This is a descriptive, prospective, and observational study. There is no formal hypothesis being tested. The study will describe the clinical and demographic characteristics of ATTR-CM patients. Also, it will describe previous treatments, cardiovascular devices, and comorbidities.

Adherence, persistence, and frequency of hospitalization will be described during the time exposure of treatment.

The change of baseline in the quality of life measured every 3 and 6 months respectively for 24 months.

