4.3 Does the protocol define how the study population will be sampled from the source population? (e.g., event or inclusion/exclusion criteria)				9.2

Comments:

PFIZER CONFIDENTIAL

CT24-WI-GL02-RF01 6.0 Non-Interventional Study Protocol Template For Primary Data Collection Study 01-

Aug-2023

Page 52 of 57

**CLINICAL AND MEDICAL CONTROLLED DOCUMENT (CMCD)
REQUIRED FORM/TEMPLATE**

Identifier	Version	Title	Effective Date
CT24-WI-GL02-RF01	6.0	NON-INTERVENTIONAL STUDY PROTOCOL TEMPLATE FOR PRIMARY DATA COLLECTION STUDY	01-Aug-2023

Section 5: Exposure definition and measurement	Yes	No	N/A	Section Number
5.1 Does the protocol describe how the study exposure is defined and measured? (e.g., operational details for defining and categorising exposure, measurement of dose and duration of drug exposure)				9.3
5.2 Does the protocol address the validity of the exposure measurement? (e.g., precision, accuracy, use of validation sub-study)				9.1
5.3 Is exposure categorised according to time windows?				9.3
5.4 Is intensity of exposure addressed? (e.g., dose, duration)				9.3
5.5 Is exposure categorised based on biological mechanism of action and taking into account the pharmacokinetics and pharmacodynamics of the drug?				
5.6 Is (are) (an) appropriate comparator(s) identified?				9.3

Comments:

Section 6: Outcome definition and measurement	Yes	No	N/A	Section Number
6.1 Does the protocol specify the primary and secondary (if applicable) outcome(s) to be investigated?				9.3
6.2 Does the protocol describe how the outcomes are defined and measured?				9.3

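### The title, research question, primary objective and section 7 promise the impact of tafamidis on quality of life, but a single cohort without a comparator, first measured after prescription, can only describe KCCQ-OS over time

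*Protocol*

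**What the plan says.** The title page reads "Impact of tafamidis use in Colombian patients diagnosed with ATTR-CM on quality of life during two years of follow-up". Section 8 repeats this as the research question, "What is the impact of tafamidis use in Colombian patients diagnosed with ATTR-CM on quality of life during two years of follow-up", and as the primary objective, "To describe the impact of tafamidis use in Colombian patients diagnosed with ATTR-CM on quality of life during two years of follow-up". The Abstract carries the same question and objective. Section 7 is the most explicit: "this study intends to measure the impact of tafamidis in quality of life, hospital frequency and mortality during the first two years of follow-up". The matching sentence in the Abstract's rationale speaks only of measuring quality of life, hospital frequency and mortality, without the word impact.

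Section 9.1 describes a non-interventional, descriptive, longitudinal cohort, and section 9.2.1 makes a tafamidis prescription an entry criterion. Section 9.7.1 states: "This is a descriptive, prospective, and observational study. There is no formal hypothesis being tested". It names change from baseline as the quality-of-life quantity. Section 9.1 places the first KCCQ at signed consent.

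In Annex 2, the item "5.6 Is (are) (an) appropriate comparator(s) identified" is ticked Yes and points to section 9.3. Item 12.1.3 (residual or unmeasured confounding) is ticked Yes and points to section 9.9.

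**The concern.** The impact of a drug on a score is the difference between the course with the drug and the course the same patients would have had without it. A single treated cohort supplies only the first. The change in KCCQ-OS mixes any drug effect with the natural course of the disease and with changes in other heart-failure treatment, which the study leaves to usual care. With the first score taken after prescription, and for many patients after the drug was started, a clean before-and-after contrast is not assured either.

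At stake is what the final report may conclude. The headline question is one the design cannot answer. The annex tells an assessor that a comparator exists and that residual confounding has been discussed, and neither is so.

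**Working it through.** **Is there a comparator anywhere in the Protocol?**

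- Sections 9.1, 9.2 and 9.2.1: one cohort, all prescribed tafamidis; no second group.
- Section 9.3, where item 5.6 points: a variable table and definitions; no comparator.
- Section 9.7.1: change from baseline.
- Section 9.7.3.2: subgroups of the same cohort, including supply delay and time on tafamidis before enrolment.
- Section 9.7.5.2: paired tests, and mixed models with visit and baseline characteristics as fixed effects; all within the cohort.
- Section 7: the placebo-controlled trial is cited as background, without KCCQ figures that could serve as a benchmark.

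Every planned contrast is therefore internal to the cohort.

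**What can be identified?** Observed change = drug effect + change that would have occurred without the drug. The Protocol plans no observation or external estimate of the second term, so the first cannot be recovered from the data, whatever the sign of the change.

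**What part of the two years is seen?**

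Inputs: the index date is the first prescription (9.1); the cohort was treated between August 2022 and August 2023 (9.2), and I take index dates from 1 August 2022 to 31 August 2023 to match; data collection runs from 15 November 2023 to 30 July 2025 (section 6); follow-up ends at month 24 from index (9.1). One month is 30.4375 days.

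- Earliest index, 1 August 2022. To 15 November 2023: 471 / 30.4375 = 15.5 months. Month 24 is 1 August 2024, so the observable span is 260 / 30.4375 = 8.5 months.
- Latest index, 31 August 2023. To 15 November 2023: 76 / 30.4375 = 2.5 months. Data collection closes on 30 July 2025, at month 699 / 30.4375 = 23.0, so the span is 623 / 30.4375 = 20.5 months.

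The delays are lower bounds and the spans upper bounds, because they assume consent on the first day of data collection.

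Table 1, as extracted, appears to mark KCCQ in the month −12 column. The extraction may be broken, and section 9.1 limits the 12-month look-back to treatments and hospitalization. A pre-index score would in any case give a before-and-after contrast, not a comparator.

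**Is confounding discussed in section 9.9?** Its six limitations concern baseline data availability, hospitalization records, small numbers, treatment begun before the study, availability of the walk test and scintigraphy, and language. None mentions a missing comparator, natural course, co-treatment or confounding.

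**The case against.** The Protocol calls itself descriptive, evaluates no hypothesis, sets no decision rules (9.7.2) and labels its regressions exploratory. It defines no causal estimand, and the primary objective begins with describe. Section 9.9 concedes that baseline quality of life may be hard to measure, section 9.1 says start dates and the timing of measurement will be considered, and concomitant treatment is recorded at follow-up visits. On this view the fault is one loose noun.

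Most of this stands, and it limits the weight of the point: no planned analysis would produce a false causal estimate. But disclaiming a test does not disclaim attribution, and "this study intends to measure the impact of tafamidis in quality of life, hospital frequency and mortality" is an attribution claim. Recording co-treatment lets it be described beside KCCQ but does not supply the missing course without the drug.

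A reader might go further in four ways that the documents do not support:

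- That every patient is on the drug throughout. Section 9.1 expressly covers patients prescribed tafamidis but not yet supplied.
- That the Protocol itself predicts decline on tafamidis because the drug only slows progression. The sentence about "other options to manage this disease which can slow disease progression to optimize quality of life and improve survival" concerns newer options for cardiac amyloidosis generally.
- That a falling KCCQ will be reported as failure and a rise as benefit. No section plans such wording, and section 9.3.1 gives the 5-, 10- and 20-point thresholds only as definitions of score change.
- That the hidden benefit can be put in points. The Protocol gives no KCCQ course with or without the drug, so any such figure would be assumed.

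**Conclusion.** The point holds as a mismatch between the stated aim and what the design can show, together with two incorrect checklist answers. It should be corrected. The remedy lies in wording and disclosure, because the planned analyses are already descriptive.

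The design supports a description of KCCQ-OS over part of the period after prescription: at most about 8.5 months for the earliest index date and 20.5 for the latest, beginning at least 15.5 and 2.5 months after prescription respectively. It supports no attribution of change to tafamidis in either direction. The month figures rest on the milestone dates and on index dates lying in August 2022 to August 2023. The conclusion on attribution rests only on the absence of a comparator.

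**What to change.** 1. Restate the title, research question, primary objective and section 7 sentence as describing KCCQ-OS over time in Colombian patients with ATTR-CM prescribed tafamidis, and carry this into the Abstract and the Annex 2 study title. The Abstract's rationale sentence already avoids the word impact.
2. Change checklist item 5.6 to No, or to N/A with a comment that this is a single-cohort descriptive study.
3. Add to section 9.9 that, without a comparator, change in KCCQ-OS cannot be separated from natural course or co-treatment. Item 12.1.3 then has something to point to.
4. State that the interim and final reports will not attribute observed change to tafamidis.

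A table of patients improved, stable and worsened would not cure this, since such proportions in a single cohort are no more attributable than the mean change.

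The cost is a wording amendment, with no new data or analyses. The downside is a less ambitious headline claim.

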9. RESEARCH METHODS

9.1. Study design

The study will be a non-interventional, descriptive, and longitudinal prospective study with primary data collection that involves sites/investigators. The patients must be diagnosed before enrollment with ATTR-CM and prescribed with tafamidis following indications approved by National Institute for Drug and Food Vigilance (INVIMA) in Colombia. The patients will be followed up from the index date until patient i) have deceased, ii) have decided to withdraw from the study, iii) have terminated of treatment, iv) have been lost to follow up, or, v) finalize the 24 months of following up, the event that happens first. The index date will be defined as the date for the first prescription of tafamidis.

The patients that were prescribed with tafamidis before August of 2023 will be recruited. In the cases where the patients were prescribed before starting the study, all previous information will be collected from the data provided by the patients. The quality of life will be evaluated when the patient accepts to participate and signs the informed consent.

Quality of life, adherence, concomitant treatment, hospitalization for any causes, cardiovascular functionality will be measured 24 months after the prescription of tafamidis. Twelve months before the index date, treatments, and frequency of hospitalization for any causes will be measured (Table 1).

There will be two sources of information. Clinical and demographic information and death at the baseline will be abstracted from the medical record while the data related to hospitalizations, cardiovascular functionality, quality of life will be collected directly from the patients using validated questionnaires and structured interviews. Thus, in this case the report form (CRF) will serve as a source document.

In patients who have been prescribed with tafamidis more than 1 month and have not received the drug by the HMO yet, the first time of administration of tafamidis will be considered in the analysis. It will be considered as limitation of access. Any delay of supply for treatment will be considered limitation of access which will be assessed during the follow-up.

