9.3. Variables

Table 2 List of variables

Variable	Role	Data source(s)	Operational definition
Date of birth	Demographic characteristics	Medical record, Interview	dd-mm-yyyy
Age	Demographic characteristics	Medical record, Interview	Time elapsed since the time of birth to signed consent form (years)
Sex assigned at birth	Demographic characteristics	Medical record, Interview	Men, female
Race (ethnicity)	Demographic characteristics	Medical record, Interview	Indigenous, Rrom, Black, None and Other
Date of symptoms of ATTR-CM	Clinical characteristic	Medical record, Interview	dd-mm-yyyy
Date of ATTR-CM diagnosis	Clinical characteristic	Medical record, Interview	dd-mm-yyyy
Genotype	Clinical characteristic	Medical record, Interview	ATTRwt; ATTRv
Scintigraphy at diagnosis (Perugini scale)	Clinical characteristic	Medical record,	Grade 0 – 3
Biopsy	Clinical characteristic	Medical record, Interview	Yes, No
Sampling biopsy	Clinical characteristic	Medical record, Interview	Heart, bone marrow, others
Sum of QRS amplitude in I, II, and III leads at diagnosis	Clinical characteristic	Medical record, Interview	mm
Sum of QRS amplitude in all six limb leads at diagnosis	Clinical characteristic	Medical record, Interview	mm
Sum of QRS amplitude in all six precordial leads at diagnosis	Clinical characteristic	Medical record, Interview	mm
Sokolow-Lyon index low voltage criteria at diagnosis	Clinical characteristic	Medical record, Interview	mm
Low QRS voltage at diagnosis	Clinical characteristic	Medical record, Interview	Yes, No

PFIZER CONFIDENTIAL

CT24-WI-GL02-RF01 6.0 Non-Interventional Study Protocol Template For Primary Data Collection Study 01-

Aug-2023

Page 24 of 57

**CLINICAL AND MEDICAL CONTROLLED DOCUMENT (CMCD)
REQUIRED FORM/TEMPLATE**

Identifier	Version	Title	Effective Date
CT24-WI-GL02-RF01	6.0	NON-INTERVENTIONAL STUDY PROTOCOL TEMPLATE FOR PRIMARY DATA COLLECTION STUDY	01-Aug-2023

Pseudo-infarct Q waves at diagnosis	Clinical characteristic	Medical record, Interview	Yes, No
Atrioventricular conduction disease (block) at diagnosis	Clinical characteristic	Medical record, Interview	Yes, No
Genetic counseling	Patient	Medical record, Interview	Yes, No
Left ventricular ejection fraction at diagnosis	Clinical characteristic	Medical record, Interview	%
N-terminal pro b-type natriuretic peptide at diagnosis	Clinical characteristic	Medical record, Interview	(pg/mL)
Heart failure at early age	Clinical characteristic	Medical record, Interview	Yes, No

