Erectile dysfunction	Clinical characteristic	Medical record, Interview	Yes, No
Glaucoma	Clinical characteristic	Medical record, Interview	Yes, No
Intravitreal deposition	Clinical characteristic	Medical record, Interview	Yes, No
angiotensin-converting enzyme inhibitors previous diagnosis	Treatment	Medical record, Interview	Yes, No
Agents acting on the renin-angiotensin system previous diagnosis	Treatment	Medical record, Interview	Yes, No
HMG COA reductase inhibitors previous diagnosis	Treatment	Medical record, Interview	Yes, No
Loop diuretics previous diagnosis	Treatment	Medical record, Interview	Yes, No
Amiodarone previous diagnosis	Treatment	Medical record, Interview	Yes, No

PFIZER CONFIDENTIAL

CT24-WI-GL02-RF01 6.0 Non-Interventional Study Protocol Template For Primary Data Collection Study 01-

Aug-2023

Page 26 of 57

**CLINICAL AND MEDICAL CONTROLLED DOCUMENT (CMCD)
REQUIRED FORM/TEMPLATE**

Identifier	Version	Title	Effective Date
CT24-WI-GL02-RF01	6.0	NON-INTERVENTIONAL STUDY PROTOCOL TEMPLATE FOR PRIMARY DATA COLLECTION STUDY	01-Aug-2023

Anticoagulation previous diagnosis	Treatment	Medical record, Interview	Yes, No
Beta blockers previous diagnosis	Treatment	Medical record, Interview	Yes, No
Calcium channel blockers previous diagnosis	Treatment	Medical record, Interview	Yes, No
Angiotensin receptor blockers previous diagnosis	Treatment	Medical record, Interview	Yes, No
Agents acting on the renin–angiotensin system after diagnosis*	Treatment	Medical record, Interview	Yes, No
HMG COA reductase inhibitors after diagnosis*	Treatment	Medical record, Interview	Yes, No
Loop diuretics after diagnosis *	Treatment	Medical record, Interview	Yes, No
Amiodarone after diagnosis*	Treatment	Medical record, Interview	Yes, No
Anticoagulation after diagnosis *	Treatment	Medical record, Interview	Apixaban, dabigatran, rivaroxaban, warfarin
Beta blockers after diagnosis*	Treatment	Medical record, Interview	Yes, No
Calcium channel blockers after diagnosis*	Treatment	Medical record, Interview	Yes, No
Angiotensin receptor blockers after diagnosis*	Treatment	Medical record, Interview	Yes, No
angiotensin-converting enzyme inhibitors previous diagnosis*	Treatment	Medical record, Interview	Yes, No
Glomerular filtration rate at diagnosis*	Clinical characteristics	Medical record, Interview	>40, <40

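### Table 2 ties clinical values and prior treatments to diagnosis, while the first two secondary objectives and section 9.1 ask for them at or before tafamidis prescription

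*Protocol*

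**What the plan says.** Section 8 sets two secondary objectives by reference to prescription: "To describe the clinical and demographic characteristics of the patients at the moment of prescription of tafamidis" and "To determine the treatment patterns to manage ATTR-CM before tafamidis prescription". Section 9.1 defines the index date as the first tafamidis prescription and states: "Twelve months before the index date, treatments, and frequency of hospitalization for any causes will be measured".

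Table 2 in section 9.3 uses other anchors:

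- Clinical severity rows carry a diagnosis label, for example "Left ventricular ejection fraction at diagnosis".
- Age is defined as "Time elapsed since the time of birth to signed consent form (years").
- Prior-treatment rows refer to the time before diagnosis, for example "Loop diuretics previous diagnosis".
- A second block of treatment rows is labelled as after diagnosis and carries an asterisk, which the footnote explains as collection per study visit.
- "angiotensin-converting enzyme inhibitors previous diagnosis" appears twice: once among the prior-treatment rows and again, with the asterisk, at the end of the per-visit block. The abstract's variable list repeats the duplicate.
- "Glomerular filtration rate at diagnosis" also carries the per-visit asterisk, and its categories are above 40 and below 40.

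**The concern.** Table 2 lists the variables to be collected, so it is the natural basis for the form. The protocol itself treats diagnosis and prescription as different moments: section 9.7.3.2 makes the interval from diagnosis to treatment start a subgroup factor. Section 9.2 dates Colombian approval to July 2022, so a patient diagnosed before then who started under that approval has a gap.

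A cohort described by LVEF, NT-proBNP and ECG values from diagnosis is not described as it was when tafamidis was prescribed. Drug use before diagnosis likewise differs from the management of known ATTR-CM before tafamidis, which is what the second objective asks about. An analysis plan written later can choose among collected values. It cannot recover values that the form never requested.

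**Working it through.** No sample size or error rate is involved. The check sets the passages side by side, counts Table 2 rows by time anchor, and does one date subtraction.

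**Anchors required.** Section 8: at prescription (characteristics) and before prescription (treatments). Section 9.1: treatments in the twelve months before the index date, which is first prescription.

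**Anchors in Table 2.**

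| Anchor | Rows | Count |
|---|---|---|
| Diagnosis, clinical | Perugini grade; three QRS sums; Sokolow-Lyon; low voltage; Q waves; AV block; LVEF; NT-proBNP; GFR | 1 + 3 + 1 + 1 + 1 + 1 + 1 + 1 + 1 = 11 |
| Consent | Age | 1 |
| Before diagnosis, treatment | Nine drug classes | 9 |
| After diagnosis, per visit | Eight drug classes | 8 |
| Labelled before diagnosis but marked per visit | ACE inhibitors | 1 |
| Prescription, clinical or prior treatment | None | 0 |

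GFR is counted by its label. Setting it aside because of its per-visit mark leaves 10 clinical rows fixed at diagnosis. Comorbidity, history, NYHA and baseline device rows carry no general time point.

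**Treatment between diagnosis and prescription.** Let g be that gap in months. The protocol does not give g, so the values below are assumptions.

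- Prior-treatment rows in Table 2, read literally, stop at diagnosis and cover 0 of the g months.
- The section 9.1 window covers min(g, 12) and leaves max(g − 12, 0).

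| g (assumed) | Covered by Table 2 prior rows | Covered by section 9.1 | Left by section 9.1 |
|---|---|---|---|
| 6 | 0 | 6 | 0 |
| 12 | 0 | 12 | 0 |
| 24 | 0 | 12 | 12 |

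For gaps up to twelve months, section 9.1 requires the whole period and the Table 2 prior rows none of it. The two passages therefore contradict each other.

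**Age.** Section 9.2 gives a treatment window of August 2022 to August 2023, and section 6 starts data collection on 15 November 2023. Assume that treatment start approximates prescription and that consent is no earlier than that date.

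- From 31 August 2023: 30 (to 30 September) + 31 (to 31 October) + 15 = 76 days, about 2.5 months.
- From 1 August 2022: 365 (to 1 August 2023) + 30 (to 31 August 2023) + 76 = 471 days, about 15.5 months.
- Section 9.1 restricts prescription to before August 2023. From 31 July 2023 the shortest gap is 31 + 76 = 107 days.

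Age at consent therefore exceeds age at prescription by at least 76 or 107 days for the latest patients, depending on which section is followed, and by at least 471 days for the earliest. Table 2 also collects date of birth and date of prescription, so age at prescription can be derived.

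**The case against.** The strongest reply is that much of the information is collected, or meant to be, despite the labels. Four readings stronger than the point made here are tempting, and on each the reply stands.

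- **ACE inhibitor use after diagnosis is lost.** The asterisk marks the disputed row as per visit, Table 1 schedules concomitant treatment during follow-up, and a broader renin-angiotensin row is also per visit. This is a labelling error.
- **The whole period between diagnosis and prescription goes unrecorded.** Section 9.1 requires the twelve months before the index date, and section 9.4 plans to abstract baseline treatment and earlier cardiac amyloidosis medication. The after-diagnosis rows could also be read to include the period, though they would then mix it with use under tafamidis and still not isolate it.
- **Every baseline row is tied to diagnosis or consent.** Comorbidity, NYHA and baseline device rows are not, and section 9.7.3.2 refers to NYHA at the start of tafamidis. None of these rows is tied to prescription in Table 2 either.
- **The exploratory model will use out-of-date severity.** Section 9.7.5.2 speaks only of baseline characteristics and names no covariates, and the age of the values is unknown.

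Section 9.9 also admits that baseline information is limited to available records, and a non-interventional study cannot order tests near prescription. That explains missing values. It does not explain asking for a different time point.

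**Conclusion.** The contradiction stands. Section 8 and section 9.1 refer to prescription. Table 2 fixes 11 clinical rows at diagnosis by their labels, age at consent, and all nine prior-treatment rows before diagnosis, with none tied to prescription. If the form follows Table 2, the first two secondary objectives are answered for the wrong time point.

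How far the results would shift cannot be stated, because the diagnosis-to-prescription gap is not given. Age is a minor part, since it can be corrected from collected dates. The ACE inhibitor and GFR rows are labelling faults that call for correction; they do not establish lost data. The primary KCCQ objective is unaffected. The conclusion assumes only that the form is built from Table 2 as worded.

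**What to change.** Align Table 2 with the index date:

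1. For each clinical row now labelled at diagnosis, record the most recent available value on or before the index date (first prescription), with its date. Keep the diagnosis value as an extra. First administration should not be the anchor: the objective and the index date both use prescription, and section 9.1 foresees supply delays of more than a month between the two.
2. Derive age at the index date from the dates already collected.
3. Label prior treatments as use in the twelve months before the index date, and concomitant treatments as use at each visit after it.
4. Relabel the asterisked ACE inhibitor row as after, in Table 2 and in the abstract.
5. Give GFR one clear time point and record it as a number, which also removes the unclassified value of exactly 40.

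The cost is form wording, using the same records and the same visits. Section 9.1 already plans to validate the form at two centers, including the variable definitions, so the change can be made there before abstraction starts. The downside is that some values near prescription will be missing. The recorded dates will show how old each available value is.
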